2.2 Secondary Objective

Secondary objectives include participant satisfaction with study procedures, the expectancy of learning skills in their assigned training group, and satisfaction with skills learned during training.

INVESTIGATIONAL PLAN

3.1 Study Design

This proposed study is a parallel assignment randomized controlled trial. Interested individuals will be initially screened for psychiatric and neurological health, medications, use of psychoactive substances, the presence of study specific contra-indications, and prior experience with meditation. Participants who meet inclusion criteria according to the initial phone-based screening will then be invited to the lab for further screening and possible participation. Upon arrival and consent, subjects will be given a urine test to screen for psychoactive drugs and a breathalyzer test to detect alcohol currently in system. Positive results will exclude participants from further participation.

Interested participants are instructed to first complete an online screening survey (through REDCap). Potential participants are then contacted for a more in-depth phone screen. When the participant comes in for the first visit, they will be screened for any current alcohol intoxication or recent substance use, followed by a mental health assessment with the Mini-International Neuropsychiatric Interview (MINI) [25]. The participant will then have blood collected by finger prick, complete the Reward-AB task, and fill out some paper surveys. During visits 2 through 5, participants will complete virtual training on either mindfulness and meditation skills, or navigating college skills. Each visit will last approximately 90 minutes, starting with the completion of a few online surveys. Visit 6 is similar to visit 1, without the health interview. Participants will be contacted one month following the date of the 6th study visit to complete online surveys.

3.2 Allocation to Treatment Groups and Blinding (if applicable)

At the end of visit 1, participants will be randomly assigned to either the training group where they will learn mindfulness and meditation skills, or the control group to learn skills in navigating college. An online random number generator will be used to determine which subject IDs will be allocated to each training group (18 people total, 9 in each group).

3.3 Study Duration, Enrollment and Number of Subjects

The entire duration of the study is expected to take no more than 3 months. About 5-6 weeks will elapse from the first visit to the 6th visit, and the inclusion of a one-month follow-up survey adds another 4 weeks, totaling a little over 2 months. Eighteen subjects are expected to be enrolled in the study, with 9 participants randomized to each of two training groups (Koru Mindfulness as the intervention training, Navigating College serving as the age- and time-matched comparison group).

3.4 Study Population

Inclusion Criteria

- High school educated; college enrolled first-year student
- Medically healthy
- Ages 18-19
- Native-English speaker (or fluent \leq 7 years old)
- Self-report of ≥ 4 lifetime binge drinking episodes (>4 drinks/2hours for females, >5 drinks/2 hours for males).

Exclusion Criteria

- Psychiatric disease (such as depression or psychosis) using the MINI [25]
- Systemic disease such as cancer, cardiovascular or inflammatory disease which could influence cognitive functioning
- Motor or visual disturbance (e.g., colorblind)

- Current use of psychoactive drugs (aside from moderate caffeine or alcohol), including prescription medications, or individuals with a known history of any substance use disorders (not including alcohol; including nicotine) or desire to seek treatment for excess substance (not including alcohol) use.

STUDY PROCEDURES

4.1 Screening/Baseline Visit procedures

Individuals who show initial interest in the study are contacted via phone or e-mail with a questionnaire containing items related to psychiatric and neurological health, medications, use of psychoactive substances, the presence of study-specific contra-indications, and prior experience with meditation. Evidence of neurological or psychiatric disorders, current use of psychoactive medications or other drugs (excluding alcohol or moderate caffeine), or prior experience with meditation will result in non-inclusion in the study. For the purpose of this study, meditation includes loving kindness, guided imagery or visualization, qi gong, and yoga. Those participants who meet inclusion criteria according to initial phone screening will be invited to the lab for further screening and possible participation. Upon arrival to the initial visit, after reading and signing the informed consent form, subjects are given a urine test to screen for psychoactive drugs (amphetamine/methamphetamine/MDMA ("ecstasy"), cocaine, opiates, THC, and PCP) and a breathalyzer test to detect alcohol currently in system (approx. 5 minutes). Results of these screening tests are not written down, but positive results will exclude participants from further participation.

4.2 Intervention procedures (by visits)

See Figure 1 for overview of study visits.

Visit 1

- Written consent, MINI interview [25], urine drug screen and breathalyzer alcohol test, C-reactive protein (CRP) assay, Reward-AB task

Visits 2-5

- Randomization to either the Koru Mindfulness (KM) intervention or the Navigating College (NC) control group.
- Each training visit will consist of the following:
 - Surveys completed online through REDCap.
 - 75 minutes of instructor-led discussion
 - Breakout sessions for participants to share their thoughts and experiences in response to instructor's prompt.

Navigating College (NC) Control Group Training

Topics discussed during each training visit include: habits, roommate issues, homesickness, the internet (week 1); strategies when sinking, study skills, getting involved, habit formation (week 2); HALT, gateway habit (week 3); and academic success tips, taking notes, and procrastination (week 4).

Koru Mindfulness (KM) Intervention Training

Topics discussed during each training visit include: belly breathing, dynamic breathing, body scan (week 1); walking meditation, gatha (week 2); guided imagery, labeling thoughts (week 3); eating meditation, and labeling feelings (week 4).

Daily Logging of Skills

Participants in the CG intervention will be asked to journal by hand or via Qualtrics every day for ≥ 10 minutes, on anything related to the topics learned during that week's training visit. Participants in the KM intervention will

be asked to practice every day for ≥ 10 minutes any mindfulness or meditation skill previously learned during training visits, in addition to logging their practice and reflection using the Koru application.

Visit 6

- Similar to visit 1, without repeating the MINI interview.

4.3 Follow- up procedures (by visits)

One month after the conclusion of visit 6, participants will be recontacted via email with a link to REDCap to complete several surveys.

4.4 Subject Completion/ Withdrawal procedures

Participants will be screened for drug and alcohol use upon arrival to visits 1 and 6. If the test results from a urine sample and breathalyzer are positive, subjects will be withdrawn from the study. If participants in the KM group are experiencing extreme discomfort during weeks when visits 2-6 take place, due to resurfacing of traumatic experiences, subjects will be withdrawn from the study and given resources (see attachments) to alleviate distress. Investigators may also terminate an individual's participation if the subject is uncooperative or otherwise behaves in a way that makes study personnel feel uncomfortable or unsafe.

4.5 Screen failure procedures

All study personnel will review study materials required for screening and will be trained in phone screening, including conducting interviews with the MINI. Personnel will also be trained in blood collection by finger prick so that any safety concerns can be addressed. Voicemails and emails left by interested participants will be checked daily.

STUDY EVALUATIONS AND MEASUREMENTS

Surveys, a CRP assay, and the Reward-AB task will be administered pre- and post-training of skills learned in the intervention or control group. Surveys will be administered at the beginning of each training visit.

5.1 Surveys

To identify factors that may contribute to individual or group differences, participants will complete several questionnaires via REDCap [26] or in person. These include the Credibility/Expectancy Questionnaire (CEQ; [27]) to measure expectancy/credibility of the intervention and control groups, self-report measures of substance use and consequences: the Alcohol Use Disorder Identification Test (AUDIT; [28]), an Alcohol-Related Blackouts Questionnaire (ARBQ; see appendix); the Carolina Alcohol Use Patterns Questionnaire [CAUPQ], which is a modified version of the Alcohol Use Questionnaire [29], the Daily Drinking Questionnaire (DDQ; [30]), the Rutgers Alcohol Problem Index (RAPI; [31]), the Brief Young Adult Alcohol Consequences Questionnaire (B-YAACQ; [32]), and the Drinking Motives Questionnaire-Revised (DMQ-R; [33]); measures of familial alcohol misuse [34], adult resilience (ARM-R; [35]), depression, anxiety and stress (DASS-21; [36]); and personality measures with the Barratt Impulsiveness Scale (BIS-11; [37]). We will also collect two questionnaire measures of behavioral flexibility: Value-Driven Attention Questionnaire (VDAQ; [38]) and the Creature of Habit Scale (COHS; [39]). Finally, we will administer two indices of mindfulness: the Five Facet Mindfulness Questionnaire (FFMQ; [22]) and the Mindful Attention Awareness Scale (MAAS; [23]).

5.2 C-Reactive Protein (CRP) Assay

Using aseptic technique, we will use a contact-activated lancet to collect a small blood sample from the finger to generate a dried blood spot (Approximately 1 cm diameter on Cytiva Watman 903 cards) for use in CRP quantification assays. Blood will be collected on the indicated cards designed for this purpose, marked with the participant's ID code which will then be air-dried, sealed in a freezer bag with silica gel packs, and placed in a designated area within a freezer. Commercially available Simple Plex microfluidic cartridge immunoassays (Bio-

Techne, <https://www.proteinsimple.com/ella.html>) will be used. In all cases, every sample is run in triplicate, and the cartridge will include positive and negative controls.

5.3 Reward-Driven Attention Bias (Reward-AB) Task

The Reward-AB task is a modified version of tasks measuring the influence of reward on visual attention [15, 20, 21]. Participants will complete the reward-conditioning phase (training) followed by the testing phase of the task. In brief, participants are instructed to indicate the orientation (vertical/horizontal) of a line inside a target circle (blue/yellow) among an array of circles. One color is associated with probabilistic (80%) monetary reward for correct responses; the other target color does not yield a monetary reward for a correct response. The training phase consists of two 60 trial runs. The testing phase of the Reward-AB task measures attentional control in the presence of a reward-conditioned distractor [21]. In this component, two colored circles appear on either side of a fixation cross. Inside each circle is a letter, either a target letter ('S' or 'P'), or a neutral letter ('E' or 'H'). Participants are instructed to pick the target letter, with correct answers not associated with any monetary reward. There are 3 runs of the testing phase, with each run consisting of 120 trials. The total duration of the task is ~30 minutes.

5.4 Safety Evaluations

The DASS-21 will be used to measure depression, anxiety and stress and will be administered at the beginning of each visit. Scores will be used to evaluate any within-subject changes that may prompt further review. The KM instructor will read logs daily and determine if any participant should be followed up with.

STATISTICAL CONSIDERATIONS

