Study Duration	
 • Each subject will undergo 4 weeks of intervention or control group training, a pre- and post-training visit, and a 1-month follow-up. • The entire study is expected to last 3 months.
Study Phases	(1) Subjects screened for eligibility and obtaining consent;
Screening	(2) Cognitive task performance, blood sample collection, surveys;
Study Treatment	(3) Four weeks of virtual training in Koru mindfulness or an age- and time-matched comparison group;
Follow-Up	(4) One-month follow up online surveys
Efficacy Evaluations	
 • Mean number of visits attended by participants and total number of journal entries.
Pharmacokinetic Evaluations	N/A
Safety Evaluations	Self-report measures of anxiety, depression, and stress will be evaluated at the beginning of each visit to determine any changes that could be in result of the intervention.
Statistical And Analytic Plan	
 • To assess the primary objective (feasibility) of the study, the primary outcome will be the count of participants in each of the 6 visits, and the number of surveys that are completed at the 1-month follow-up contact. • To assess the secondary objective (participant compliance), the secondary outcome will be measured by total journal entries submitted during the 4 weeks of intervention training.
DATA AND SAFETY MONITORING PLAN	The Co-Investigators will review participants' experiences with study procedures on a weekly basis. Meditation practice may elicit discomfort if traumatic memories resurface or the participant is experiencing high stress. The Koru teacher is trained in trauma-sensitive mindfulness and has implemented this awareness in the design of the visits. Nonetheless, the teacher will regularly check in with students to address any concerns.

BACKGROUND AND RATIONALE

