6.3 Statistical Methods

The total number of eligible participants will be used as a measure of successful recruitment strategies and feasibility of enrollment criteria. The mean number of self-report training or journaling days recorded by participants and the total number of visits attended by each participant will be used as measures of compliance with study procedures. The number of times discomfort is reported by participants with any training procedure will be used as a measure of safety. A within-subjects ANOVA will be used to analyze the change in DASS-21 scores across the training visit weeks, including the total score and scores for all 3 subscales. A 1-Sided t-Test will be used to analyze the mean difference in CEQ score between the intervention and control group.

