6.4 Sample Size and Power

A power analysis is not applicable for this pilot study due to the small number of subjects intended to be recruited solely for the purpose of determining the feasibility of conducting described study procedures.

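### The DASS-21 is collected as the opening part of each visit, and the plan provides no score, and no way to analyse a gap, when a training visit is missed

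*Combined protocol and SAP*

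**What the plan says.** The synopsis, under Safety Evaluations, and section 5.4 give the same timing: "Self-report measures of anxiety, depression, and stress will be evaluated at the beginning of each visit" and "The DASS-21 will be used to measure depression, anxiety and stress and will be administered at the beginning of each visit". The paragraph that opens Study Evaluations and Measurements says of surveys in general: "Surveys will be administered at the beginning of each training visit." Section 3.1 places them inside the training visit: "Each visit will last approximately 90 minutes, starting with the completion of a few online surveys." Section 4.2 lists, as one component of each of visits 2 to 5, "Surveys completed online through REDCap".

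The scores have two uses. Section 6.3 plans the analysis: "A within-subjects ANOVA will be used to analyze the change in DASS-21 scores across the training visit weeks", for the total and the three subscales; section 6.2 lists the DASS-21 as a secondary endpoint. Sections 5.4 and 6.5 use within-person change, and 6.5 specifically the change between one visit and the next, for individual review and stopping.

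Missed visits are foreseen: section 6.1 measures retention at each visit, and section 6.3 counts the visits each participant attends. The only survey link that the plan describes sending outside a visit is the one-month follow-up in section 4.3. No make-up window and no rule for missing DASS-21 scores is given.

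**The concern.** Followed as written, a missed class means no DASS-21 score for that week, although the form could be completed from anywhere. This has two consequences.

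- **Group analysis.** A standard within-subjects ANOVA needs a score from each participant at every time point. One missed class out of four removes the person, along with the scores they did give. Those who remain are the regular attenders. The plan itself recognises that training may cause distress (synopsis; sections 1.3 and 4.4). If distress is one reason for staying away, the completers will look better than the full group.
- **Individual review.** The comparison between successive visits needs both scores. One missed class removes the comparison into that visit and the one out of it, and the plan does not say what is compared instead.

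The trial is also meant to inform a larger study. Whether DASS-21 scores can be collected from people who miss a class is something a feasibility study could learn, and under the current plan it would not.

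**Working it through.** The plan states no attendance rate, DASS-21 coverage or power figure, so there is no figure of its own to reproduce. Section 3.3 gives the sample: "Eighteen subjects are expected to be enrolled in the study, with 9 participants randomized to each of two training groups" (9 + 9 = 18). Section 6.4 says: "A power analysis is not applicable for this pilot study".

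**Inputs.** From the documents: N = 18 and four training visits (visits 2 to 5), hence 18 × 4 = 72 person-visits. Assumed: attendance *a* at each class, set at 90% or 80%, and no score without attendance.

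**Formulas.**
- Expected scores in any one week: 18*a*.
- Missed person-visits: 72(1 − *a*).
- Participants with all four scores, absences independent: 18*a*⁴.
- Fewest with all four, each absence falling on a different person: 18 − 72(1 − *a*).
- Most with all four, the same people always absent: 18*a*.
- Participants with both scores for a given pair of successive training visits, absences independent: 18*a*².

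| Quantity | *a* = 0.90 | *a* = 0.80 |
|---|---|---|
| Scores per week | 18 × 0.90 = 16.2 | 18 × 0.80 = 14.4 |
| Missed person-visits of 72 | 7.2 | 14.4 |
| All four, independent | 18 × 0.656 = 11.8 | 18 × 0.410 = 7.4 |
| All four, absences fully spread | 18 − 7.2 = 10.8 | 18 − 14.4 = 3.6 |
| All four, absences fully clustered | 16.2 | 14.4 |
| Both scores of a successive pair, independent | 18 × 0.81 = 14.6 | 18 × 0.64 = 11.5 |

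With constant attendance the expected number of scores is the same every week. What shrinks is the set of people with all four.

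**Individual comparisons.** Six visits give five successive comparisons (1–2, 2–3, 3–4, 4–5, 5–6). Missing any one of visits 2 to 5 removes two of the five.

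**Effect of sending the form to absentees.** If a share *s* of absentees completes it, coverage per week becomes *a* + (1 − *a*)*s*. With an assumed *s* = 0.5:
- *a* = 0.90 gives coverage 0.95, and 18 × 0.95⁴ = 14.7 with all four scores, against 11.8.
- *a* = 0.80 gives coverage 0.90, and 18 × 0.90⁴ = 11.8, against 7.4.

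**The case against.** The strongest reply is that the plan is silent rather than restrictive. The start of the visit is a timing, the form is online, and nothing forbids an absentee from completing it. That is correct: a reader might infer a rule that only attenders are scored, but no section states one. What stands is that the surveys are described as part of the visit, that the plan spells out a remote link where it intends one (section 4.3), and that none is described for a missed class.

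A reader might also infer that coverage falls week by week. The documents give no attendance rate or trend. Intermittent absence at a constant rate leaves weekly coverage flat; a decline would need attendance itself to decline.

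Nor do the documents support the idea that the weekly trend would compare different people in different weeks. The named analysis is within-subjects and would normally use the same completers throughout. The risk is lost numbers and selection of completers.

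Finally, the DASS-21 is not the sole safety measure. Logs are read daily (section 5.4; Safety Management), the co-investigators review participants' experiences weekly (synopsis), discomfort reports are counted (section 6.3), and section 6.5 also acts on journals, logs and reported distress. None of these needs a DASS-21 score. They are a partial backstop: logs depend on participants continuing to submit them, section 5.4 names only the mindfulness instructor as daily reader, control participants may journal on paper, and none of these routes fills a missing score.

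It is also fair to say that this is a secondary endpoint in an unpowered pilot, and that reporting attendance by visit would make much of the gap visible afterwards. Seeing the gap does not recover the scores.

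**Conclusion.** The point holds as a gap in data collection and analysis. The plan provides no DASS-21 score when a training visit is missed, and no method for the incomplete data that follow. Under the assumed 90% or 80% attendance, the complete-case ANOVA would rest on about 12 or 7 of 18 participants if absences are independent, with ranges of 10.8 to 16.2 and 3.6 to 14.4 according to clustering. These figures assume equal attendance at the four classes and no score without attendance; the attendance values are illustrations, since attendance is what the pilot sets out to measure. That distress drives absence is plausible but not shown by the documents, so the direction of any selection is a risk and not a finding. The primary feasibility objective is unaffected. The change is worth making because it is cheap and recovers secondary-endpoint and safety data that may be missing for reasons related to distress.

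**What to change.** - **Sections 5.4 and 3.1:** send the DASS-21 REDCap link to every randomised participant who has not withdrawn, on each scheduled class date, whether or not they attend, with a reminder the next day.
- **Section 6.3, analysis:** analyse by scheduled week with a method that keeps participants with incomplete scores, for example a linear mixed model with week as a factor. Such a model still assumes that missingness is explained by the scores observed, so it complements collection from absentees and does not replace it.
- **Section 6.3, reporting:** give the number of scores out of the number randomised, by week and arm.

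The cost is an automated invitation and reminder in a system already in use, and a few sentences of text. Some scores will be completed away from class time, and some absentees will still not respond. The change leaves the individual review and stopping rules as they are; what is compared after a missed visit remains for the investigators to state.

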6.1 Primary Endpoint

1. Feasibility assessment [Time Frame: every week]
 - a. The feasibility of the study design will be measured using the total number of eligible participants, and retention rate for each visit, in addition to the one-month follow-up survey of enrolled participants. Compliance with individual training will be determined by the mean number of journal entries submitted per week in each group, due to previous evidence demonstrating an association between amount of homework completed and positive outcomes [40].

